9. EFFICACY ANALYSES

All efficacy analyses will be conducted on the Infused population.

9.1. Primary Efficacy Analysis

9.1.1. Spleen and Liver Volume

All spleen and liver volumes will be listed, together with %CFB. For spleen volume, any increase from baseline \geq 25%, and for liver volume, any increase from baseline \geq 20%, will be flagged on the listing.

Figures displaying %CFB over time, with study week on the x-axis, along with arithmetic or geometric means, will also be provided. For spleen volume, a horizontal reference line will be added to indicate a 25% increase from baseline, and for liver volume, a horizontal reference line will be added to indicate a 20% increase from baseline.

9.1.2. Hemoglobin Concentration

Observed values and absolute change from baseline in hemoglobin values will be listed. Any decreases from baseline of >2 (g/dL) will be flagged on the listing.

Hemoglobin values relative to baseline, derived as post-baseline value/baseline value, will also be listed, and any values <0.8, indicating hemoglobin concentrations < 80% of the baseline value, will be flagged on the listing.

Figures displaying individual values over time, with study week on the x-axis, along with arithmetic or geometric means, will also be provided. A horizontal reference line will be added to indicate a CFB of -2 (g/dL).

A figure displaying individual values relative to baseline over time, with study week on the x-axis, along with arithmetic or geometric means, will also be provided. A horizontal reference line will be added at 0.8 to indicate any hemoglobin concentration < 80% of the baseline value.

9.1.3. Platelet Count

Platelet counts will be listed. Any values $<35 (10^{9}/L)$ will be flagged on the listing.

Platelet counts relative to baseline, derived as post-baseline value/baseline value, will also be listed, and any values <0.8, indicating platelet count <80% of the baseline value, will be flagged on the listing.

Figures displaying individual values over time, with study week on the x-axis, along with arithmetic or geometric means, will also be provided. A horizontal reference line will be added at $35 (10^9/L)$.

A figure displaying individual values relative to baseline over time, with study week on the xaxis, along with arithmetic or geometric means, will also be provided. A horizontal reference line will be added at 0.8 to indicate any platelet count < 80% of the baseline value.

9.1.4. Lyso-Gb1 in Plasma

Observed values and absolute change from baseline in Lyso-Gb1 plasma levels will be listed. Any values >1.2 ng/mL will be flagged on the listing.

Figures displaying individual values over time, with study week on the x-axis, along with arithmetic or geometric means, will also be provided.

A horizontal reference line will be added at the ULN of 1.2 ng/mL.

Dashed horizontal reference line will be added at the LLQ of 0.6 ng/mL and at the ULQ of 1000 ng/mL.

9.2. Primary Engraftment Analysis

9.2.1. VCN in Peripheral Blood

VCN in peripheral blood assessed by qPCR will be listed.

A figure displaying individual values over time, with study week on the x-axis, along with arithmetic or geometric means.

A horizontal reference line will be added at the LLQ of 0.0027 average copies/cell.

9.2.2. VCN in Bone Marrow Aspirate

VCN in bone marrow stem and progenitor cells assessed by qPCR will be listed.

A figure displaying individual values over time, with study week on the x-axis, along with arithmetic or geometric means.

A horizontal reference line will be added at the LLQ of 0.0027 average copies/cell.

9.3. Secondary Efficacy Analyses

9.3.1. GCase Enzyme Activity in Peripheral Blood, DBS and Plasma

Observed values and absolute change from baseline in GCase enzyme activity level values in peripheral blood, plasma and DBS will be listed.

For GCase enzyme activity level values in peripheral blood, any values $<4.0 \mu mol/g/h$ will be flagged on the listing.

For GCase enzyme activity level values in plasma, any values ${<}0.4~\mu mol/L/h$ will be flagged on the listing.

For GCase enzyme activity level values in DBS, any values <4.1 μ mol/g/h will be flagged on the listing.

Figures displaying individual values over time, with study week on the x-axis, along with arithmetic or geometric means, will also be provided for peripheral blood, plasma and DBS.

On the figure of absolute values of GCase enzyme in peripheral blood, a horizontal reference line will be included at the LLN (4.0 μ mol/g/h) and at 15% of LLN (0.6 μ mol/g/h). Dashed

horizontal reference lines will be included at the LLQ (0.3 μ mol/g/h) and the ULQ (100 μ mol/g/h).

On the figure of absolute values of GCase enzyme in plasma, a horizontal reference line will be included at the LLN (0.4 μ mol/L/h) and at 15% of LLN (0.06 μ mol/L/h). Dashed horizontal reference lines will be included at the LLQ (0.2 μ mol/L/h) and at the ULQ (200 μ mol/L/h).

On the figure of absolute values of GCase enzyme in DBS, a horizontal reference line will be included at the LLN (4.1 μ mol/g/h) and at 15% of LLN (0.615 μ mol/g/h). Dashed horizontal reference lines will be included at the LLQ (1.0 μ mol/g/h) and at the ULQ (200 μ mol/g/h).

9.3.2. ERT

The rationale, frequency, and doses of ERT, including between Weeks 26-52 (inclusive) will be listed.

9.3.3. Immunogenicity

All individual immunogenicity data will be presented in data listings, including the presence or absence of anti-GCase antibodies, and change from baseline in anti-GCase antibody isotypes and titers.

In case of presence/increase of anti-GCase antibodies, any investigation of the presence of neutralizing anti-GCase antibodies, as well as the clinical relevance of their presence with regards to (i) reduction of enzyme activity in blood, plasma and cells; (ii) reduction in transduced progenitor cells and VCN; (iii) autoimmune-mediated cytopenias will be discussed in the CSR.

9.3.4. BMD

Observed values and absolute change from baseline in BMD values assessed by DXA will be listed.

Figures displaying individual values over time, with study week on the x-axis, along with arithmetic or geometric means, will also be provided.

9.3.5. Chitotriosidase Enzyme Activity in Plasma

Observed values and absolute change from baseline in chitotriosidase enzyme activity level values in plasma will be listed. Any values $>38.1 \mu mol/L/h$ will be flagged on the listing.

Figures displaying individual values over time, with study week on the x-axis will also be provided.

A horizontal reference line will be added at the ULN of 38.1 µmol/L/h.

Dashed horizontal reference line will be added at the LLQ of 0.8 μ mol/L/h and at the ULQ of 150 μ mol/L/h. Any values at or above ULQ will not be included on the figure and a footnote will describe their exclusion.

9.3.6. BMB

Observed values and absolute change from baseline in BMB score assessed by bone MRI will be listed.

Figures displaying individual values over time, with study week on the x-axis, along with arithmetic or geometric means, will also be provided.

9.4. Exploratory Efficacy Analyses

9.4.1. SF-36

Observed values and absolute change from baseline in the eight SF-36 subscale scores (i.e., Vitality, Physical Functioning, Bodily Pain, General Health Perceptions, Physical Role Functioning, Emotional Role Functioning, Social Role Functioning, and Mental Health) and 2 component summary scores (Physical Functioning and Mental Functioning) will be listed.

9.4.2. **BPI-SF**

Observed values and absolute change from baseline in BPI-SF questionnaire scores for pain severity and pain interference will be listed.

9.4.3. Exploratory biomarkers for Gaucher disease in serum, plasma, urine, and whole blood derived leukocytes, or subpopulations

Observed values and absolute change from baseline in exploratory biomarkers for Gaucher disease in serum, plasma, urine, and whole blood derived leukocytes, or subpopulations will be listed.

9.4.4. Exploratory genomic biomarkers for Gaucher disease in whole blood at Screening (ie, CHIT1, gene encoding chitotriosidase)

As knowledge of Type 1 Gaucher disease pathophysiology and related biomarkers continues to evolve, back-up plasma and urine samples will be collected and archived for possible future nongenomic and genomic biomarker testing either at specialized laboratories or a Biorepository site. These samples will be destroyed 5 years after the CSR is finalized.

9.4.5. Average VCN and ISA results in Whole Blood and Bone Marrow

Average VCN and ISA results in whole blood and bone marrow will be listed.

For subjects with an average VCN in PBLs ≥ 0.01 as determined by the central laboratory, suggesting $\geq 1\%$ of the sampled blood cells are vector-positive with an average of 1 copy/diploid genome (c/dg), testing for vector ISA will also take place.

10. SAFETY ANALYSES

All safety analyses will be conducted on the Safety and Infused populations.

No inferential statistical testing will be performed for safety variables.

10.1. Primary Safety Analysis

10.1.1. Adverse Events

An adverse event (AE) is any untoward medical occurrence in a subject administered a pharmaceutical product and which does not necessarily have a causal relationship with the IMP. An AE can therefore be any unfavorable or unintended sign (including an abnormal laboratory finding), symptom, or disease temporally associated with the IMP, regardless of whether the event is causally related to the IMP.

The definition of an AE also covers:

- Medication errors and uses outside what is foreseen in the protocol, including accidental overdose, if an AE results from the error;
- Any Grade 3 or higher platelet count, grade 3 or higher WBC count, and grade 2 or higher neutrophil count (grade determined by CTCAE) regardless of whether considered clinically significant by Investigator report;
- Fertility-related events, considered an AE of special interest (AESI) for the study.

Adverse events will be coded using MedDRA® version 23.0.

10.1.1.1. Treatment-emergent Adverse Events

Any AE that started prior to mobilization with G-CSF is considered a pre-treatment AE and is listed, but not included in tabulations (except for tabulations using study periods where Pre-Mobilization is included). However, pre-treatment AEs that worsen/increase in severity after the subject started mobilization with G-CSF will be recorded as new AEs and consequently will be regarded as treatment emergent and thus will be included in the tabulations.

10.1.1.2. Serious Adverse Events

An SAE is any untoward medical occurrence or effect that:

- Results in death
- Is life threatening, that is any event that places the subject at immediate risk of death from the event as it occurred. It does not include an event that, had it occurred in a more severe form, might have caused death
- Results of in-patient hospitalisation or a prolongation of existing hospitalisation, excluding admission for social or administrative reasons (see below)
- Results in a persistent or significant disability/incapacity, where disability is a substantial disruption of a person's ability to conduct normal life functions
- Results in congenital anomaly/birth defect in the offspring of a subject who received AVR-RD-02
- Is an important medical event that may not result in death, be life threatening, or require

hospitalisation, but that, based upon appropriate medical judgment, may jeopardise the subject and may require medical or surgical intervention to prevent one of the outcomes listed in this definition.

Examples of such medical events include allergic bronchospasm requiring intensive treatment in an emergency room or at home, blood dyscrasias or convulsions that do not result in in-patient hospitalisation, or the development of drug dependency or drug abuse.

For all SAEs, the Investigator must provide the following:

- Appropriate and requested follow-up information in the time frame detailed in Protocol
- Causality of the SAE(s)
- Outcome of the SAE(s)
- Redacted medical records and laboratory/diagnostic information.

10.1.1.3. Adverse Drug Reaction or Adverse Reaction

All untoward and unintended responses to an investigational medicinal product. The phrase responses to an investigational medicinal product means that a causal relationship between the investigational medicinal product and an adverse event is at least a reasonable possibility, i.e., the relationship cannot be ruled out.

10.1.1.4. Unexpected Adverse Reaction

An adverse reaction, the nature or severity of which is not consistent with the applicable product information (e.g., investigator's brochure for an unauthorized AVR-RD-02 or summary of product characteristics for an authorized product).

Suspected unexpected serious adverse reactions (SUSARs) are serious events that are not listed in the Investigator's Brochure and that are identified as related to study treatment.

10.1.1.5. Adverse Event Severity

AE severity will be graded using the CTCAE v4.03. The CTCAE is a descriptive terminology utilized for AE reporting. A grading (severity) scale is provided for each AE term.

Grade refers to the severity of the AE. The CTCAE displays Grades 1 through 5, with unique clinical descriptions of severity for each AE based on this general guideline:

- **Grade 1** Mild; asymptomatic or mild symptoms; clinical or diagnostic observations only; intervention not indicated.
- Grade 2 Moderate; minimal, local or noninvasive intervention indicated; limiting age-appropriate instrumental activities of daily living (ADL)
- **Grade 3** Severe or medically significant, but not immediately life-threatening; hospitalization or prolongation of hospitalization indicated; disabling; limiting self-care ADL.
- Grade 4 Life-threatening consequences; urgent intervention indicated.
- **Grade 5** Death related to AE.
 - Instrumental ADL refer to preparing meals, shopping for groceries or clothes, using the telephone, managing money, etc.

• Self-care ADL refer to bathing, dressing and undressing, feeding self, using the toilet, taking medications, and not bedridden.

Change in severity of an AE should be documented based on specific guidelines in the eCRF completion guidelines.

Severity and seriousness must be differentiated: severity describes the intensity of an AE, while the term seriousness refers to an AE that has met the criteria for an SAE.

10.1.1.6. Adverse Event Relationship

The relationship between an AE and AVR-RD-02, mobilization (G-CSF or plerixafor), apheresis, conditioning (busulfan), anti-convulsant medication(s), study procedures or underlying disease will be assessed based on clinical experience and classified according to the following:

- Definite
 - Event or laboratory test abnormality, with plausible time relationship to drug intake
 - Cannot be explained by disease or other drugs
 - Response to withdrawal plausible (pharmacologically, pathologically)
 - Event definitive pharmacologically or phenomenologically (i.e., an objective and specific medical disorder or a recognized pharmacological phenomenon)
 - Rechallenge satisfactory, if necessary
- Probable
 - Event or laboratory test abnormality, with reasonable time relationship to drug intake
 - Unlikely to be attributed to disease or other drugs
 - Response to withdrawal clinically reasonable
 - Rechallenge not required
- Possible
 - Event or laboratory test abnormality, with reasonable time relationship to drug intake
 - Could also be explained by disease or other drugs
 - Information on drug withdrawal may be lacking or unclear
- Unlikely
 - Event or laboratory test abnormality, with a time to drug intake that makes a relationship improbable (but not impossible)
 - Disease or other drugs provide plausible explanations
- Unrelated
 - Event or laboratory test abnormality is plausibly related to the subject's clinical state, underlying disease, or the study procedure/conditions
 - Time relationship to drug intake makes a relationship unreasonable
 - Other obvious causes for event or laboratory test abnormality exist
- Unknown
 - Report suggests an AE; however, cannot be judged at this time because information is insufficient or contradictory

- More data for proper assessment is needed, or additional data is under examination
- Not applicable (N/A)
 - Report suggests an AE; however, the need to assess causality is not practical or of value, due to the event itself, or to the circumstances surrounding the event

Adverse events classified as "Not applicable" will not be included in tabulations.

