2.2.2. Safety Endpoints

2.2.2.1. Primary Safety Endpoints

Primary safety endpoints:

- Incidence and severity of AEs, incidence of serious adverse events (SAEs), and incidence and severity of AEs of interest, including drug-product related AEs, infections, and malignancy
- Change from Baseline in clinical laboratory values relevant to safety
- Change from Baseline in vital signs
- Change from Baseline in ECG findings and Weeks 26 and 52

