10.1.1.8. Adverse Event Tabulations

All AEs (serious and non-serious) occurring after completion of the informed consent process and before the end of study will be included and classified by system organ class (SOC) and preferred term (PT) using MedDRA^{*} v23.0. Date imputation algorithm from Section 5.7.15 will be employed to partial dates.

A data listing of all AEs, including pre-treatment AEs (as defined in Section 5.7.15), will be provided including verbatim term, SOC, PT, toxicity, relationship to mobilization (G-CSF or plerixafor), relationship to apheresis, relationship to conditioning, relationship to AVR-RD-02, relationship to study procedure, relationship to underlying disease, date/time and day of onset, date/time and day of resolution, duration, possible co-medication, treatment given to treat the adverse event, the outcome, whether the event was an SAE, and whether it led to withdrawal. The derived study onset period used to tabulate AEs by onset will also be included. AEs prior to G-CSF for Mobilization will be flagged on this listing. In addition, a separate listing of all serious AEs will be provided, with any SAEs prior to treatment (Mobilization) flagged.

Deaths, if any, will be listed for subject, date/time, primary cause and autopsy finding.

Listings will be sorted by subject identification number, onset date/time, SOC, and PT. If the onset date is completely missing, then these events will be presented first. If the onset date is missing a month or a day then partial dates for AEs will be imputed as per Table 3 to allow AEs to be sorted appropriately. Imputed dates will not be listed.

The AE tabulations, unless stated otherwise, will be based on TEAEs. Therefore, all pretreatment AEs will be excluded from the tabulations, unless stated otherwise. However, pretreatment AEs that worsen/increase in severity after G-CSF for Mobilization will be recorded as new AEs and consequently will be regarded as treatment emergent and thus will be included in the tabulations.

Descriptive statistical methods will be used to tabulate the TEAE data including both the number of subjects and number of events. TEAE tables including the number of events will be presented in the following order: number of subjects, (percentage of subjects) and [number of events].

TEAEs will be presented in descending order of frequency across all subjects.

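### SAP 10.1.1.6 leaves adverse events with causality rated Not applicable out of tabulations without limiting this to the causality tables, so as written it can remove real events from the primary safety tables

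*SAP*

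**What the plan says.** SAP 10.1.1.6 opens by naming what is rated for each event: "The relationship between an AE and AVR-RD-02, mobilization (G-CSF or plerixafor), apheresis, conditioning (busulfan), anti-convulsant medication(s), study procedures or underlying disease". That makes seven factors. The scale runs from Definite to Unrelated, followed by Unknown and Not applicable. The last category is described as: "Report suggests an AE; however, the need to assess causality is not practical or of value, due to the event itself", or because of the surrounding circumstances. Protocol section 9.2.1.3 (Table 3) offers investigators the same category. The SAP section closes by saying that events classified as Not applicable "will not be included in tabulations".

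Three other places in the SAP bear on this:

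- Section 2.2.2.1, primary safety endpoints: "Incidence and severity of AEs, incidence of serious adverse events (SAEs), and incidence and severity of AEs of interest". No condition on causality is attached to incidence or severity overall.
- Section 10.1.1.8, the section that governs the tables: "All AEs (serious and non-serious) occurring after completion of the informed consent process and before the end of study will be included", with classification by system organ class and preferred term. It adds: "The AE tabulations, unless stated otherwise, will be based on TEAEs".
- Section 5.7.15 defines a treatment-emergent event by when it began or worsened relative to the start of mobilization. Causality plays no part.

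**The concern.** An event for which the investigator found no value in assessing causality is still an event. If its causality code removes it from the tables, the reported incidence and severity no longer describe what happened to the subjects. Incidence and severity of adverse events is a primary endpoint of this first-in-human study, so the main safety tables are the ones affected.

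There is also a programming problem. One event carries several ratings, and the sentence treats the event as having a single classification. Two programmers could both follow the SAP and produce different primary safety tables.

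**Working it through.** The documents state no figure on this point and plan no hypothesis test, so the check is a comparison of passages followed by one argument about direction.

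**1. What does the SAP mean by tabulations?** Section 10.1.1.1 says that events starting before mobilization are listed but kept out of tabulations, and then makes an exception for tables by study period that include Pre-Mobilization. There the word covers adverse event tables in general, and an exception is written where one is wanted. Section 10.1.1.8 uses the word in the same general way. The sentence in 10.1.1.6 has no exception.

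**2. Would a causality-only reading give the sentence any work to do?** Very little. In the overall summary of 10.1.1.8, related means possible, probable or definite. The tables by causal relationship use the same three levels. Whether a subject was exposed to a given treatment is handled by restricting the denominator to evaluable subjects. An event rated Not applicable for a factor is therefore already outside the related count for that factor.

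**3. What does each reading do to one event?** Take a hypothetical treatment-emergent event rated Probable for conditioning, Unrelated to AVR-RD-02 and Not applicable for apheresis.

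| Tables covered | Rating that triggers exclusion | Result |
|---|---|---|
| All | Not applicable on any factor | Dropped from the overall, class/term/grade and onset tables, and even from the count related to conditioning |
| All | Not applicable for AVR-RD-02 | Kept |
| All | Not applicable on every factor | Kept |
| Related counts only | Factor by factor | Kept in every incidence table; not counted as related to apheresis, which it would not have been anyway |

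The SAP text does not choose among the first three rows. Only the fourth agrees with sections 2.2.2.1, 5.7.15 and 10.1.1.8 for every pattern of ratings: under the second and third rows, an event rated Not applicable for AVR-RD-02, or on every factor, would still be dropped.

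**4. Which way does the effect run?** For a given term, incidence = n/N, where n is the number of subjects with at least one counted event. Under 10.1.1.8 the denominator N is the population total or, in the onset tables, the number of subjects who took part in the period. The rule leaves N unchanged. If k subjects have all of their events under that term excluded, incidence becomes (n − k)/N with 0 ≤ k ≤ n. The change is −k/N, which is never positive. Likewise, a subject's maximum grade can stay the same or fall, but cannot rise. Neither k nor the analysed N is given in the documents.

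**5. Does another text settle it?** Protocol 11.8.3 restricts summaries to treatment-emergent events and has no such exclusion, but SAP section 1 gives the SAP precedence on analysis. SAP 10.4, on changes to planned analyses, does not mention the exclusion. Within the SAP, the phrase about tabulations being based on treatment-emergent events unless stated otherwise could be taken to let 10.1.1.6 override. That would remove the contradiction only by accepting the loss of events.

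**The case against.** The best defence is the sentence's position. It directly follows the causality scale, in a section on relationship, and the section that governs the tables says that all events are included. The onset tables are described as covering all events as well as treatment-emergent ones. On that view the author meant only that Not applicable ratings are not shown in the relationship outputs. This may well have been the intention. It is a reason to say so in the text, because the words do not carry the limit and the narrow reading leaves them nearly redundant.

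Two stronger inferences are tempting, and the documents support neither.

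- A reader might infer that events during mobilization, apheresis or conditioning would naturally be rated Not applicable to a product not yet given, so that the loss is greatest before infusion. Section 10.1.1.6 places an implausible time relation to dosing under Unrelated. How sites would code such events is not stated, and no claim about which phase loses most is warranted.
- A reader might attach a percentage by dividing one subject by the planned 8 to 16. That is an approximate planned size which SAP 3.2.2 allows to change. SAP section 1 records that the study stopped early, and section 5.1 that no treatment-naïve subjects were enrolled. The planned range does not describe the analysed population.

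It also stands that the harm is bounded. All adverse events are listed with grade, seriousness, outcome and onset period, serious events and deaths have their own listings, and nothing is inferential.

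**Conclusion.** The rule is wrong as written and should be corrected. It excludes events by causality code from tables whose purpose is to count events regardless of cause, it conflicts with SAP 10.1.1.8, and it cannot be programmed without guessing which rating triggers it. The effect on tabulated incidence and maximum severity is downward or nil. Its size is unknown and may be zero if no event was rated Not applicable.

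The conclusion rests on reading the sentence as it stands and on the SAP's own general use of the word tabulations. It does not depend on any assumption about how often or when the category was used, and it does not imply that the sponsor intended to reduce reported incidence.

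**What to change.** Replace the closing sentence of SAP 10.1.1.6 with:

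*AEs rated Not applicable for a given treatment or procedure are excluded only from the related-AE count for that treatment or procedure; they are included in all incidence, severity, seriousness and onset-period tables.*

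This takes one sentence and needs no new data. Tabulated incidence may come out slightly higher than under the literal rule. SAP section 1 allows amendment before database lock. After lock, the change can be documented and justified in the clinical study report.
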